3.2.2. Clinical Safety Laboratory Data

Safety laboratory tests will be performed as described in the protocol.

The investigator must review the laboratory report, document this review, and record any clinically significant changes occurring during the study in the AE section of the CRF. Clinically significant abnormal laboratory test findings are those that are not associated with the underlying disease, unless judged by the investigator to be more severe than expected for the participant's condition.

Baseline will be the measurement taken on Day -1.

To determine if there are any clinically significant laboratory abnormalities, the hematological, clinical chemistry (serum) and urinalysis safety tests will be assessed against the criteria specified in the sponsor reporting standards. The assessment will take into account whether each participant's baseline test result is within or outside the laboratory reference range for the particular laboratory parameter.

3.2.3. Vital Signs Data

Single supine blood pressure and pulse rate measurements will be taken at times detailed in the SoA given in the protocol.

Baseline for these measures will be defined as the last pre-dose measurement in each study period.

The following endpoints will be determined:

- Change from baseline (CFB) in systolic and diastolic BP and pulse rate
- The minimum and maximum post-dose systolic and diastolic BP and pulse rate
- The maximum increase and decrease from baseline over all measurements taken post-dose for systolic and diastolic BP and pulse rate

The maximum increase from baseline will be calculated by selecting the maximum change from baseline over the respective period, except in the case where a participant does not show an increase. In such an instance, the minimum decrease should be taken. Similarly, the maximum decrease from baseline will be determined by selecting the minimum value of the change from baseline. In cases where a participant does not show a decrease, the minimum increase should be taken.

If 3 of more participants have unplanned measurements at the same timepoint these may be summarized in addition to the planned timepoints.

3.2.4. Electrocardiogram Data

A single 12-lead ECG will be obtained on all participants at times detailed in the SoA given in the protocol. ECG endpoints include heart rate, QT interval, PR interval and QTcF and QRS

complex. If not supplied QTcF will be derived using Fridericia's heart rate correction formula [1].

QTcF (msec) = QT (msec) / (RR) $^{1/3}$ where RR (sec) = 60/HR (if RR not provided).

Baseline will be defined as the last measurement prior to administration of study treatment on Period 1 Day 1.

The following endpoints will be determined:

- Change from baseline in QT, QTcF, PR, QRS interval and heart rate
- The maximum post-dose QTcF, heart rate, PR and QRS interval
- The maximum increase from baseline over all measurements taken post-dose for QTcF, heart rate, PR and QRS values

The maximum increase from baseline will be calculated by selecting the maximum change from baseline over the respective period, except in the case where a participant does not show an increase. In such an instance, the minimum decrease should be taken.

3.3. Other Safety Endpoint(s)

Not applicable

3.4. Other Endpoint(s) (or, Exploratory Endpoints)

3.4.1. Additional Plasma PK Parameters

Additional plasma PF-07817883 PK parameters, as described in Table 4, will be determined:

Table 4. Additional PF-07817883 Plasma PK Parameters

Parameter	Definition	Method of Determination	Analysis Scale	Analysis Method
T	Time for C _{max}	Observed directly from data as time of first occurrence	R	D
C ₁₂	Concentration observed at 12 hours	Observed directly from data	In	D
V _z /F*	Apparent volume of distribution	Dose/(AUC _{inf} x k _{el})	In	D
CL/F*	Apparent clearance	Dose/AUC _{inf}	In	D
t _½ *	Terminal elimination half-life	Log _e (2)/k _{el} , where k _{el} is the terminal phase rate constant calculated by a linear regression of the loglinear concentration-time curve. Only those data points judged to describe the terminal log-linear decline will be used in the regression.	R	D

Table 4. Additional PF-07817883 Plasma PK Parameters

Parameter	Definition	Method of Determination	Analysis	Analysis
			Scale	Method

^{*=}if data permits.

Abbreviations: D=displayed with descriptive statistics as outlined in Table 5 in Section 6.1; In=natural-log transformed; R = raw (untransformed).

3.4.2. Drug Product Acceptability

The acceptability attributes of PF-07817883 will be evaluated by the participant using a Drug Product Acceptability Questionnaire (as shown in Appendix 8 of the protocol). In each period, each participant will complete the Drug Product Acceptability Questionnaire immediately following dosing.

Each item will be evaluated on a Likert scale with numeric categories to capture the level of agreement or disagreement with a statement about drug-product appearance, palatability, swallowability, or overall impression of taking the drug product (1=strongly agree, 5=strongly disagree). The frequency of each response for each item will be summarized and reported.

3.5. Baseline Variables

Not applicable

4. ANALYSIS SETS (POPULATIONS FOR ANALYSIS)

Data for all participants will be assessed to determine if participants meet the criteria for inclusion in each analysis population prior to unblinding and releasing the database and classifications will be documented per standard operating procedures.

Participant Analysis Set	Description
Enrolled	"Enrolled" means a participant's, or their legally authorized representative's, agreement to participate in a clinical study following completion of the informed consent process and randomization to study intervention.
Safety analysis set	All participants randomly assigned to study intervention and who take at least 1 dose of study intervention in at least one treatment period. Participants will be analyzed according to the product they actually received.
PK Concentration analysis set	The PK concentration population is defined as all participants randomized and treated who have at least 1 concentration value in at least 1 treatment period.

Participant Analysis Set	Description
PK Parameter analysis set	The PK parameter analysis population is defined as all participants randomized and treated who have at least 1 of the PK parameters of interest in at least 1 treatment period.

5. GENERAL METHODOLOGY AND CONVENTIONS

5.1. Hypotheses and Decision Rules

There is no statistical hypothesis testing planned for this study, and no statistical decision rules will be applied.

5.2. General Methods

Unless otherwise stated, all summaries and plots will be presented by treatment.

5.2.1. Analyses for Continuous Endpoints

Continuous variables will be presented using summary statistics: number of observations, arithmetic mean, standard deviation, CV%, median, minimum, and maximum values.

Log transformed continuous variables will be presented using summary statistics: number of observations, arithmetic mean, median, CV%, standard deviation, minimum, maximum, geometric mean, and geometric CV%.

5.2.2. Analyses for Categorical Endpoints

Categorical variables will be presented using summary statistics: number of observations and percentages.

5.2.3. Mixed Effects Model

A mixed effects model with sequence, period and treatment as fixed effects and participant within sequence as a random effect will be used.

Estimates of the adjusted (least squares) mean differences (Test-Reference) and corresponding 90% confidence intervals will be obtained from the model. The adjusted mean differences and 90% confidence intervals for the differences will be exponentiated to provide estimates of the ratio of adjusted geometric means (Test/Reference) and 90% confidence intervals for the ratios. Treatment A will be the Reference treatment while Treatments B, C, and D will be the Test treatments.

The mixed effects model will be implemented using SAS Proc Mixed, with REML estimation method and the Kenward-Roger degrees of freedom algorithm.

Residuals from the models will be examined for normality and the presence of outliers via visual inspection of plots of residuals vs predicted values and normal probability plots of residuals, but these will not be included in the clinical study report. If there are major deviations from normality or outliers (where studentized [conditional] residuals are greater than 3 or less

than -3), then the effect of these on the conclusions may be investigated through alternative transformations and/or analyses excluding outliers. Justification for any alternative to the planned analysis will be given in the report of the study if applicable.

Example code is shown in Appendix 1.

5.3. Methods to Manage Missing Data

For the analysis of safety endpoints, the sponsor data standard rules for imputation will be applied.

5.3.1. Concentrations Below the Limit of Quantification

In all PK data presentations (except listings), concentrations below the limit of quantification (BLQ) will be set to zero. In listings, BLQ values will be reported as "<LLQ", where LLQ will be replaced with the value for the lower limit of quantification (LLQ).

5.3.2. Deviations, Missing Concentrations and Anomalous Values

For PK summary tables and plots of mean/median profiles, statistics will be calculated having set concentrations to missing if 1 of the following cases is true:

- 1. A concentration has been collected as ND (i.e., not done) or NS (i.e., no sample),
- 2. A deviation in sampling time (10% deviation within 10 hours following dosing) is of sufficient concern or a concentration has been flagged anomalous by the pharmacokineticist/statistician.

If a PK parameter cannot be derived from a participant's concentration data, the parameter will be coded as NC (i.e., not calculated). (Note that NC values will not be generated beyond the day that a participant discontinues). In summary tables, statistics will be calculated by setting NC values to missing; and statistics will be presented for a particular dose with ≥3 evaluable measurements.

If an individual participant has a known biased estimate of a PK parameter (due for example to an unexpected event such as vomiting before all the compound is adequately absorbed in the body), this will be footnoted in summary tables and will not be included in the calculation of summary statistics or statistical analyses.

6. ANALYSES AND SUMMARIES

For all presentations, study day will refer to the day within a particular treatment period, unless otherwise specified.

6.1. Primary Endpoint(s)

Plasma PK parameters for PF-07817883, as described in Section 3.1 and the additional plasma PK parameters listed in Section 3.4.1, will be listed and summarized descriptively by treatment, as applicable, for participants in the PK Parameter Set (as defined in Section 4). Missing values will be handled as detailed in Section 5.3.

Each PK parameter will be summarized by treatment using the summary statistics as specified in the table below:

Table 5. Summary Statistics for PF-07817883 Plasma PK Parameters

	Parameter	Summary Statistics
Primary	AUC _{last} , AUC _{inf} *, and C _{max}	N, arithmetic mean, median, CV%, standard deviation, minimum, maximum, geometric mean and geometric CV%.
Tertiary	T _{max}	N, median, minimum, maximum.
	C_{12} , V_z /F*, and CL/F*	N, arithmetic mean, median, CV%, standard deviation, minimum, maximum, geometric mean, and geometric CV%.
	t _{1/2} *	N, arithmetic mean, median, CV%, standard deviation, minimum, maximum.

^{*:} if data permit

Supporting data from the estimation of AUC_{inf} and $t_{1/2}$ will be listed by treatment: terminal phase rate constant (k_{el}); goodness of fit statistic from the log-linear regression (r^2); the percent of AUC_{inf} based on extrapolation ($AUC_{extrap\%}$); and the first, last, and number of time points used in the estimation of k_{el} . This data may be included in the clinical study report.

For AUC_{inf} (if data permit), AUC_{last} , and C_{max} , a listing of the individual participant ratios (test/reference) will be provided. Box and whisker plots for AUC_{inf} (if data permit), AUC_{last} , and C_{max} , will be plotted by treatment and overlaid with geometric means.

The following will be presented for the plasma concentration data using the PK Concentration Set (as defined in Section 4):

- a listing of all concentrations sorted by participant ID and nominal time post-dose. The concentration listing will also include the actual times. Deviations from the nominal time will be given in a separate listing.
- a summary of concentrations by nominal PK sampling time and treatment. where the set of statistics will include n, mean, median, standard deviation, coefficient of variation (CV), minimum, maximum and the number of concentrations above the lower limit of quantification.
- mean and median concentration time plots (on both linear and semi-log scales) against nominal time post-dose by treatment. One plot for each scale will be presented, which will include all doses in the same plot colored by treatment.
- individual concentration time plots by treatment allocation (on both linear and semi-log scales) against actual time post-dose (there will be separate spaghetti plots for each treatment, with a line for each participant per scale).
- individual concentration time plots by participant (on both linear and semi-log scales) against actual time post-dose (there will be separate spaghetti plots for each treatment, with a line for each participant per scale).

The scale used for the x-axis (time) of these plots will be decided on review of the data and will depend on how long PF-07817883 concentration is quantifiable in the matrix.

The nominal PK sampling time will be used for summary statistics and relevant median plots, whereas for individual participant plots by time, the actual PK sampling time will be used.

For the primary objective, natural log transformed AUC_{inf} (if data permit), otherwise AUC_{last}, and C_{max} for PF-07817883 will be analyzed using a mixed effect model with sequence, period and treatment as fixed effects and participant within sequence as a random effect in Periods 1 to 4. Estimates of the adjusted mean differences (test-reference) and corresponding 90% confidence intervals will be obtained from the model. The adjusted mean differences and 90% confidence intervals for the differences will be exponentiated to provide estimates of the ratio of adjusted geometric means (test/reference) and 90% confidence intervals for the ratios. Treatment A will be the Reference treatment while Treatments B, C, and D will be the Test treatments.

6.2. Secondary Endpoint(s)

All safety analyses will be performed on the safety population.

6.2.1. Adverse Events

AEs will be listed and summarized by treatment and overall and in accordance with sponsor reporting standards using the safety population defined in Section 4.

Incidence and severity of TEAE tables will additionally be produced ('All causality' and 'Treatment related,' separately) to summarize the total number of adverse events by preferred term, which will be reported by treatment and overall, in accordance with sponsor reporting standards using the safety analysis set defined in Section 4.

The AEs will be presented sorted in descending frequency based on the overall number of AEs (by preferred term or system order class as appropriate) across treatments.

6.2.2. Clinical Safety Laboratory Data

Safety laboratory data will be listed and summarized by treatment and overall, in accordance with the sponsor reporting standards using the safety analysis set defined in Section 4. Baseline is as defined in Section 3.2.2.

Data collected at screening that are used for inclusion/exclusion criteria, will be considered source data, and will not be required to be reported, unless otherwise noted.

In summary and listing tables, laboratory abnormalities occurring pre-dose on Day -1 for each period starting with Period 2, will be attributed to the dose from the previous period (e.g., an occurrence pre-dose at Period 2 Day -1 will be attributed to the Period 1 dose). Unplanned assessment will be excluded from the safety summary but will be listed.

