6.2.3. Vital Signs Data

Absolute values and changes from baseline (as defined in Section 3.2.3) in supine systolic and diastolic blood pressure and pulse rate will be listed, and summarized by treatment and

timepoint, according to sponsor reporting standards using the safety population defined in Section 4. Tables will be paged by parameter.

Mean absolute values and mean changes from baseline for systolic and diastolic blood pressure and pulse rate will be plotted against time point. On each plot, there will be 1 line for each treatment with all treatments on the same plot. Corresponding individual participant plots of changes from baseline will also be produced for each treatment.

Maximum decrease from baseline for supine systolic and diastolic blood pressures and respiratory rate and maximum increase from baseline for supine pulse rate and temperature will be summarized by treatment, according to sponsor reporting standards.

Maximum and minimum absolute values and changes from baseline (as defined in Section 3.2.3) for supine vital signs will also be summarized descriptively by treatment using categories as defined in Appendix 2. Numbers and percentages of participants meeting the categorical criteria will be provided. All planned and unplanned post dose time points will be counted in these categorical summaries. All values meeting the criteria of potential clinical concern will be listed.

Individual participant profiles will be created for those participants meeting the sponsor abnormality criteria – including absolute values, change from baseline and percent change from baseline.

Values meeting the categorical criteria occurring pre-dose on Day 1 for each period starting with Period 2, will be attributed to the dose from the previous period (e.g., an occurrence pre-dose at Period 2 Day 1 will be attributed to the Period 1 dose).

Data collected at screening that are used for inclusion/exclusion criteria, will be considered source data, and will not be required to be reported, unless otherwise noted. Unplanned assessment will be listed but will be excluded from safety summary except for categorical summaries.

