6.2.4. Electrocardiogram Data

Absolute values and changes from baseline in QT, heart rate, QTcF, PR and QRS will be summarized by treatment and timepoint using sponsor reporting standards, using the safety analysis set defined in Section 4. Baseline is as defined in Section 3.2.4. Tables will be paged by parameter.

Mean changes from baseline in QT, heart rate and QTcF will be plotted against time postdose. On each plot there will be one line for each treatment. Corresponding individual plots of changes from baseline will also be produced for each treatment.

Changes from baseline in QTcF will also be plotted separately against drug concentrations of PF-07817883. This will be a scatter plot for all observations where QTcF and drug concentration are recorded. Different symbols will be used for each treatment.

Maximum increase from baseline for QTcF, heart rate, PR and QRS values will be summarized by treatment according to sponsor reporting standards.

ECG endpoints and changes from baseline (QTcF [1], PR and QRS) will also be summarized descriptively by treatment (if applicable) using categories as defined in Appendix 2. Numbers and percentages of participants meeting the categorical criteria will be provided. All planned and unplanned postdose time points will be counted in these categorical summaries. The frequency of uncorrected QT values above 500 ms will also be tabulated.

Individual participant profiles will be created for those participants meeting the sponsor's abnormality criteria – including absolute values, change from baseline and percent change from baseline.

Values meeting the categorical criteria occurring pre-dose on Day 1 for each period starting with Period 2, will be attributed to the treatment from the previous period (e.g., for cohort 1, an occurrence pre-dose at Period 2 Day 1 will be attributed to the Period 1 dose).

Listings of participants with any single post-dose value >500msec will also be produced for QTcF.

Data collected at screening that are used for inclusion/exclusion criteria, will be considered source data, and will not be required to be reported, unless otherwise noted. Unplanned assessments will be listed but will be excluded from safety summary except for categorical summaries.

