Appendix 1. PK Analyses – Example of SAS Code for mixed effects model

An example of the PROC MIXED code:

```
proc mixed data=tab.pk method=reml;
class seq period trt participant;
model &var=seq period trt/ residual ddfm=KR;
random participant(seq);
Ismeans trt;
estimate 'B vs A' trt -1 1 0 0 /cl alpha=0.1;
estimate 'C vs A' trt -1 0 1 0 /cl alpha=0.1;
estimate 'D vs A' trt -1 0 0 1 /cl alpha=0.1;
run;
```

Appendix 2. Categorical Classes for ECG and Vital Signs of Potential Clinical Concern Categories for QTcF

Degree of Prolongation	Mild (ms)	Moderate (ms)	Severe (ms)
Absolute value	>450-480	>480-500	>500
Increase from baseline		30-60	>60

Categories for PR and QRS

PR (msec)	max. ≥300	
PR (msec) increase from	Baseline >200 and max. ≥25%	Baseline ≤200 and max.
baseline	increase	≥50% increase
QRS (msec)	max. ≥140	
QRS (msec) increase from	≥50% increase	
baseline		

Categories for Vital Signs

Systolic BP (mm Hg)	min. <90	
Systolic BP (mm Hg) change from baseline	max. decrease ≥30	max. increase ≥30
Diastolic BP (mm Hg)	min. <50	
Diastolic BP (mm Hg) change from baseline	max. decrease ≥20	max. increase ≥20
Supine pulse rate (bpm)	min. <40	max. >120

Measurements that fulfill these criteria are to be listed in the report.

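### SAP 6.2.2 leaves every unplanned laboratory result out of the safety summary, whereas 6.2.3 and 6.2.4 count unplanned vital signs and ECGs in categorical summaries; a minor inconsistency to align

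*SAP*

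**What the plan says.** Three neighbouring SAP sections deal with unplanned safety assessments.

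- **Laboratory data (SAP 6.2.2):** "Unplanned assessment will be excluded from the safety summary but will be listed". No exception follows.
- **Vital signs (SAP 6.2.3):** "Unplanned assessment will be listed but will be excluded from safety summary except for categorical summaries". The same section adds: "All planned and unplanned post dose time points will be counted in these categorical summaries".
- **ECG (SAP 6.2.4):** "Unplanned assessments will be listed but will be excluded from safety summary except for categorical summaries". It also counts planned and unplanned post-dose values in its categorical tables.

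SAP 3.2.2 sets up an abnormality assessment for labs: "To determine if there are any clinically significant laboratory abnormalities, the hematological, clinical chemistry (serum) and urinalysis safety tests will be assessed" against criteria held in the sponsor's reporting standards. SAP 6.2.2 expects such abnormalities in summary tables as well as listings; its attribution rule opens "In summary and listing tables, laboratory abnormalities occurring pre-dose on Day -1 for each period starting with Period 2".

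In the schedule of activities (Protocol 1.3), post-dose safety labs are planned only on Day 3 of the last period and at early termination. Protocol 8.3.4 allows unscheduled labs at any time when a safety question arises.

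**The concern.** Laboratory abnormalities, vital signs and ECGs are named together in the secondary safety endpoint, yet the SAP applies a stricter exclusion to labs and gives no reason. Apart from an early termination visit, any lab drawn after dosing in Periods 1 to 3 is unplanned. Under the literal text, a criteria-meeting result found only on such a sample does not enter the laboratory-abnormality count, while an equivalent unplanned ECG or blood pressure value would enter its own count. At stake is the completeness of one descriptive safety table. No hypothesis test or PK comparison depends on it.

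**Working it through.** The plan gives no figure to reproduce on this point. The check is a comparison of the text, with some arithmetic for context.

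**1. Is the rule different?** Yes. The SAP 6.2.2 sentence matches those in 6.2.3 and 6.2.4 in substance, but lacks the exception for categorical summaries.

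**2. Does the exclusion have a table to act on?** Probably. Appendix 2 is titled "Categorical Classes for ECG and Vital Signs of Potential Clinical Concern" and has no laboratory classes. However, SAP 3.2.2 assesses labs against sponsor criteria, and SAP 6.2.2 refers to laboratory abnormalities in summary tables. The layout and counting rules of those tables are not in the documents.

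**3. Does the sampling schedule explain the difference?** No. Planned assessments after the first dose (Protocol 1.3) are:

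| Assessment | Periods 2 to 4, pre-dose | Period 4 Day 3 | Early termination |
|---|---|---|---|
| Vital signs | yes | yes | yes |
| ECG | not required | yes | yes |
| Safety labs | none | yes | yes |

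Labs and ECGs have the same planned post-dose schedule but different rules.

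**4. Does the adverse event route explain it?** No. SAP 3.2.2 requires the investigator to "record any clinically significant changes occurring during the study in the AE section of the CRF", but Protocol 7.1.2 and 8.3.1.1 provide a comparable route for ECGs and vital signs.

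**5. Which results are affected?** A result is lost from the count only if all of these hold: it meets a sponsor criterion, it comes from an unplanned sample, and no planned sample from that participant shows the abnormality. If it also generates no adverse event, it is missing from the adverse event tables too. The undercount is the number of participants in this position. The documents do not give that number, and it may be 0. The direction is fixed: leaving results out cannot raise a count.

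**6. Context only.** Twelve participants × 4 periods = 48 doses. If all complete, 12 of the 48 have a planned lab after the dose and before any later dose (12/48 = 25%), which is 3 per treatment from the Period 4 column of the design table. With 8 completers there are 8 such labs, or 2 per treatment, apart from early termination visits. At the minimum 48 h washout, doses fall at 0, 48, 96 and 144 h and the planned lab at 144 + 48 = 192 h. It therefore comes 192, 144, 96 and 48 h after the doses of Periods 1, 2, 3 and 4. These figures describe the schedule. They do not measure the undercount and would be the same if SAP 6.2.2 were amended.

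**The case against.** The best defence is structural. In SAP 6.2.3 and 6.2.4 the exception refers to tables built on the Appendix 2 categories, and Appendix 2 has none for labs, so the wording in 6.2.2 may be deliberate. Labs are delegated to sponsor standards, which may already say how unplanned results are counted. This stands as a limit on certainty. It does not settle the matter, because SAP 6.2.2 itself puts laboratory abnormalities in summary tables and then excludes unplanned results from the summary without qualification.

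A second argument is that for-cause samples come from selected participants, so adding them distorts comparisons between formulations. That is true, but the SAP already accepts it for vital signs and ECGs, and a footnote can deal with it.

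A reader might infer that an unplanned laboratory abnormality would appear nowhere except in a listing. The documents do not support that. Clinically significant changes go to the adverse event page. Protocol 10.3.1 also requires an adverse event record when an abnormal result comes with symptoms, further testing, intervention or a change in dosing. Protocol 9.3.5 separately commits to describing laboratory abnormalities of potential clinical concern, without restricting this to planned samples, and SAP 2.1 declares no modifications to the protocol's analysis plan. A reader might also take the 36 doses without their own planned lab (48 − 12) as lost safety data. They are not: Protocol 4.2 states that post-dose labs and ECGs in every period were left out to limit participant burden.

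**Conclusion.** The inconsistency is real and minor. As written, SAP 6.2.2 can omit from the laboratory-abnormality count a criteria-meeting result seen only on an unplanned sample, chiefly in Periods 1 to 3. The size of the omission cannot be computed and may be zero. The conclusion assumes that the safety summary in 6.2.2 includes abnormality counts and that the sponsor standards do not override the sentence; neither can be confirmed from the documents. Safety is descriptive, about 12 participants are planned, every unplanned value is listed, and the primary PK analysis is unaffected.

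**What to change.** In SAP 6.2.2:

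- State that unplanned labs are listed and excluded from by-timepoint descriptive summaries.
- State that laboratory-abnormality counts against the sponsor criteria use all post-dose results, planned and unplanned, each assigned to the last treatment received before the sample, in line with the adverse event rule in SAP 3.2.1.
- Show the number of participants tested beside the number with an abnormality.
- Footnote results from unplanned samples as not comparable between formulations.

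The cost is a few sentences and one table footnote, with no new data or visits. The downside is that for-cause samples come from selected participants and the count may look slightly less favourable.

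A separate editorial point: the attribution rule in SAP 6.2.2 covers Day -1 labs from Period 2 onward, but the schedule of activities has Day -1 activities only before Period 1. The two should be reconciled.
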